The comparison of pain scores (cyclic and non-cyclic, combined and separately) at PTC versus SC will be used to evaluate the potential change in pain scores after the completion of double-blind study intervention, without the intervention of MK-7264 as in the SC (ie, participants are only exposed to rescue medication).

The PGIC is an exploratory endpoint, to be assessed at the end of TRC2. It is a 7-point scale in the eDiary to collect a participant's rating of overall change in her ERP relative to her condition before initiation of the treatment.

The EHP-5 is an exploratory endpoint to be assessed at baseline and at the end of TRC2. It is an endometriosis-specific questionnaire in the eDiary to assess participant's health-related quality of life at the beginning of the run-in period and at the end of TRC2.

Participants will also answer questions in the eDiary to assess the impact of pelvic pain by determining if their pelvic pain causes any limitations in work/school, physical activities, leisure/social activities, and sleep. Responses to these questions, the EHP-5, and the PGIC will help to determine the effect of pelvic pain on health-related quality of life.

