9.4 Analysis Endpoints

9.4.1 Efficacy Endpoints

Primary Efficacy Endpoint

- Average daily pelvic pain scores (cyclic and non-cyclic) during TRC2

Secondary Efficacy Endpoints

- Average daily cyclic pelvic pain scores during TRC2
- Average daily non-cyclic pelvic pain scores during TRC2

Exploratory Efficacy Endpoints

- Average daily use of naproxen sodium rescue medication by number of tablets taken for daily pelvic pain (cyclic and non-cyclic, combined and separately) during TRC2
- Proportion of participants with at least 1-point (2, or 3) reduction in average daily pelvic pain score (cyclic and non-cyclic, combined and separately) as compared to baseline
- Proportion of participants with at least 1-point (2, or 3) reduction in average daily pelvic pain score (cyclic and non-cyclic, combined and separately) as compared to baseline, and no increase in the average daily use of rescue medication by number of tablets
- Proportion of participants with at least 1-point (2, or 3) reduction in average daily pelvic pain score (cyclic and non-cyclic, combined and separately) as compared to baseline, no increase in the average daily use of rescue medication by number of tablets, and no use of concomitant pain medication
- Proportion of participants with at least 1-point (2, or 3) reduction in average daily pelvic pain score (cyclic and non-cyclic, combined and separately) as compared to baseline, no increase in the average daily use of rescue medication by number of tablets, and no use of concomitant pain medication for ERP
- Average daily pelvic pain scores (cyclic and non-cyclic) during PTC
- Average daily pelvic pain scores (cyclic and non-cyclic) during TRC1

- Number of days with no impact (score=0) of endometriosis-related pain at TRC2 on each of the following items, separately: work/school, physical activities, leisure/social activities, and sleep.
- Patient's Global Impression of Change ratings at TRC2
- Endometriosis Health Profile-5 at TRC2

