3. ANALYTICAL AND METHODOLOGICAL DETAILS

3.1 STATISTICAL ANALYSIS PLAN SUMMARY

Key elements of the SAP are summarized below. The comprehensive plan is provided in Sections 3.2-3.12.

Study Design Overview	A Phase 2a, Proof of Concept, Randomized, Double-blind, Placebo-controlled Clinical Trial, to Evaluate the Efficacy and Safety of MK-7264 in Women with Moderate to Severe Endometriosis-related Pain
Treatment Assignment	Participants will be randomized in a 1:1 ratio to MK-7264 or placebo. Randomization will be stratified according to the following factors: moderate pelvic pain (score of ≥ 5 to < 8 on the NRS in the eDiary at baseline cycle) or severe pelvic pain (score of ≥ 8 on the NRS in the eDiary at baseline cycle).
Analysis Populations	Efficacy: Full Analysis Set (FAS) population. Safety: All Participants as Treated (APaT) population.
Primary Endpoint	Efficacy: Average daily pelvic pain scores (cyclic and non-cyclic) during TRC2. Safety: 
 • The proportion of participants with adverse events (AEs) • The proportion of participants with an AE which leads to discontinuation
Statistical Methods for Key Efficacy Analyses	The primary analysis approach will be conducted utilizing the longitudinal analysis of covariance (ANCOVA) model. In this model, the response vector consists of the change from baseline in the average daily pelvic pain score during Treatment Cycle 1 (TRC1) and Treatment Cycle 2 (TRC2). The model will include factors for average pelvic pain scores at baseline cycle, stratum, treatment, cycle, interaction of stratum-by-cycle, and the interaction of treatment-by-cycle as covariates. The model will use all available daily scores for calculating average pain scores during TRC1 and TRC2. The least squares (LS) mean change

	
from baseline with the associated standard errors (SEs) will be displayed for each treatment group. Estimated treatment differences (MK-7264 – placebo) along with corresponding 95% CIs will also be presented.

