The EHP-5 is an endometriosis-specific questionnaire to assess the participant's health-related quality of life. Participants will respond by selecting one of these five categorical responses- "never", "rarely", "sometimes", "often", "always"- at the beginning of the run-in period (Visit 3) and at the end of TRC 2 (Visit 6) on 5 items from the core questionnaire. The EHP-5 responses will be summarized in terms of frequencies and percentages in the cross-classification table for each of 5 items.

- The Patient's Global Impression of Change (PGIC) ratings:

The PGIC is a 7-point scale collecting a participant's rating of overall change in her ERP relative to her condition before initiation of the treatment. Participants rate their change as "much better", "better", "a little better", "the same," "a little worse", "worse", or "much worse". Proportion of subjects with improvements (either "much better" or "better" or "a little better" on the PGIC scale) at TRC2 will be analyzed using the stratified Miettinen and Nurminen method (1985) [1].

- Impact score of pelvic pain:

Fraction of days with no impact (score=0) of endometriosis-related pain (ERP) during BC and TRC2 will be summarized on each of work/school, physical activities, leisure/social activities, and sleep items.

Additionally, change from baseline in average daily pelvic pain score (cyclic and non-cyclic, combined and separately) during TRC2 on days with rescue medication versus days without use rescue medication will also be summarized.

Handling of Missing Data

Sensitivity analyses will be conducted to incorporate methods for handling missing data (i.e., no eDiary entry for either TRC1 or TRC2). The missing data will be imputed based on jump-to-reference method, that is, the missing scores after dropout time in treatment group will be imputed from the placebo group.

The longitudinal data analysis (LDA) method assumes that data are missing at random (MAR). In this study, it is expected that missing at random and missing completely at random (MAR/MCAR) mechanisms will underlie most of the missingness, and the proportion of data missing not at random (MNAR), driven solely by unobserved values of the

study endpoints, will be small. The multiple imputation (MI) approach will be used to assess the robustness of the primary analysis approaches.

Jump-to-reference (J2R) Multiple-imputation Analysis

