3.9 SAMPLE SIZE AND POWER CALCULATIONS

166 participants (83 in each group) will be randomized in this study, and the expected drop-out rate is 15%. Then 140 evaluable participants (70 participants in each group) will provide 84% power to detect a difference of 1 point between MK-7264 and placebo during TRC2, in change from baseline of the average daily pelvic pain score in the NRS, with one IA conducted when 84 participants have been enrolled and completed TRC2 or 60% of the participants who are expected to complete TRC2. This power calculation is based on a two-sided test with Type I error 0.05. The drop-out rate is from previous trials in chronic cough of MK-7264, and there is limited data to estimate the drop-out rate for ERP. Table 4 provides the power calculations for different assumptions of drop-out rate with the randomized participants.

Table 4 Power Calculation Based on Different Dropout Rates

Number of Randomized Participants	Dropout Rate	Number of Evaluable Participants	Power
166	10%	149	86%
	12%	146	85%
	15% (expected)	140	84%
	20%	132	82%

The assumption of the 1 point difference between MK-7264 and placebo, and the common standard deviation (SD) of 2 units are based on a publication by Diamond [2]. [Table 5](#) provides the power calculations for different assumptions of SD with the sample size.

Table 5 Power Calculation for Different Assumptions of SD with 140 Evaluable Subjects

Difference	SD	power
1	2.5	66%
1	2	84%
1	1.5	98%
1	1	100%

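### The protocol SAP and sSAP give EHP-5 only item-by-item frequency tables, with no baseline-adjusted comparison between arms, although the data for one are collected

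*Combined protocol and SAP*

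**What the plan says.** Protocol Section 9.4.1 lists "Endometriosis Health Profile-5 at TRC2" among the exploratory efficacy endpoints, and sSAP Section 3.4.1 repeats it. Protocol Section 4.2.1.1 says that EHP-5, the PGIC and the daily impact questions together "will help to determine the effect of pelvic pain on health-related quality of life". The Schedule of Activities collects EHP-5 at Visit 3, Visit 6 and the Discontinuation visit (unless that falls after Visit 6).

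Protocol Section 9.6 leaves methods for exploratory objectives to the sSAP, and sSAP Section 3.6 places them in Section 3.6.1. That section describes five core items with responses from never to always, and then gives the analysis: "The EHP-5 responses will be summarized in terms of frequencies and percentages in the cross-classification table for each of 5 items".

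The next entry, PGIC, is dichotomised as improved or not and compared between arms by the stratified Miettinen–Nurminen method. The daily impact items are summarised only.

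The opening of protocol Section 9 says that separate plans, outside the sSAP, will cover participant-reported outcomes. No such plan is among the documents.

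**The concern.** The responses are ordered and there is a pre-treatment measurement on the same instrument, so a baseline-adjusted treatment comparison is available. The stated method uses none of this. It gives no treatment difference, no interval and no rule for missing forms, and it does not say that the tables are split by arm.

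At stake is what a proof-of-concept trial can learn from its endometriosis-specific quality-of-life instrument. Without a pre-specified comparison, anyone who wants a treatment contrast must choose after unblinding how to collapse the tables.

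**Working it through.** **Inputs from the documents (sSAP Sections 3.1 and 3.9)**

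- Allocation: "Participants will be randomized in a 1:1 ratio to MK-7264 or placebo".
- Size and stated power: "140 evaluable participants (70 participants in each group) will provide 84% power to detect a difference of 1 point".
- Effect and spread, for the pain NRS only: "The assumption of the 1 point difference between MK-7264 and placebo, and the common standard deviation (SD) of 2 units".
- Test: "This power calculation is based on a two-sided test with Type I error 0.05".
- EHP-5 effect size, SD, pre-post correlation and inter-item correlation: none given. All are assumed below.

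**Step 1. The plan's own figure.** For two means, power = Φ(d·√(n/2) − 1.960), with d the standardised difference and n the number per arm. Here d = 1/2 = 0.5 and n = 70, so 0.5 × √35 = 2.958, and Φ(2.958 − 1.960) = Φ(0.998) = 84.1%. Allowing for the futility look gives 83.7%. The stated 84% reproduces.

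**Step 2. A baseline-adjusted five-item total.** Let d be the effect in units of the change-score SD and ρ the correlation between the Visit 3 and Visit 6 totals. ANCOVA multiplies the SD by f = √((1+ρ)/2), so power = Φ(d·√(n/2)/f − 1.960). For d = 0.5 and ρ = 0.5, f = 0.866, and Φ(2.958/0.866 − 1.960) = Φ(1.456) = 93%.

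| Assumed d, n per arm | Unadjusted change | ρ = 0.3 | ρ = 0.5 | ρ = 0.7 |
|---|---|---|---|---|
| 0.5, n = 70 | 84% | 96% | 93% | 89% |
| 0.5, n = 60 | 78% | 93% | 89% | 84% |
| 0.4, n = 70 | 66% | 84% | 78% | 73% |
| 0.3, n = 70 | 43% | 60% | 54% | 49% |
| 0.2, n = 70 | 22% | 31% | 28% | 25% |

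The scaling matters. If d is in units of the Visit 6 SD, then f = √(1−ρ²). For ρ = 0.3, 0.5 and 0.7 and n = 70, power is then 87%, 93% and 99% at d = 0.5, and 46%, 54% and 70% at d = 0.3. The plan states its pain effect for change from baseline, so the table uses the change-score SD.

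**Step 3. Check with ordinal items.** Five items were simulated from a latent normal with cut points −1.5, −0.7, 0.2 and 1.0. The placebo shift was 0.4 SD, the pre-post correlation 0.4–0.6 and the inter-item correlation 0.4–0.6, with the effect on the latent total held fixed. ANCOVA of the summed 0–4 scores gives, at 70 per arm, 87–95% power for an effect of 0.5 and 46–58% for 0.3. A repeat with another seed and no stratum term gave 86–94% and 47–57%. With the Step 2 table, the ranges are roughly 87–96% at 0.5 SD and 46–60% at 0.3 SD.

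**Step 4. Total against single items.** If the total has effect 0.5 and the inter-item correlation is r, one item has effect 0.5/√(5/(1+4r)). For r = 0.3 to 0.7 that is 0.33 to 0.44, with unadjusted power of 50–73%. Five independent item tests at 5% would carry a familywise error of 1 − 0.95⁵ = 23%. One total is the more efficient summary, if the instrument's scoring rule allows it.

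**The case against.** **A separate plan is reserved.** This stands in part. A reader might infer that EHP-5 will never be scored or compared between arms. The documents do not support that, because the unseen plan for participant-reported outcomes could contain such an analysis. What can be said is that the protocol SAP and sSAP do not specify one, although sSAP 3.6.1 is where exploratory methods were to be placed and it already states a method for EHP-5 without pointing elsewhere.

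**The endpoint is exploratory.** This stands. The objective in protocol Section 3 is to assess EHP-5, without the comparison with placebo named in the primary and secondary objectives. A reader might infer that the quality-of-life objective cannot be answered. That goes too far: PGIC belongs to the same objective and is compared between arms. EHP-5 is also not alone, since the impact items are only summarised.

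**Continuous exploratory endpoints already get a model like the primary one.** This does not cover EHP-5. The sSAP calls its responses categorical, defines no total, and gives it a specific sentence that governs.

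**Item-level reporting is defensible.** This stands in part. The documents contain no EHP-5 scoring rule, and nothing shows that an equal-weight sum is valid. The total must therefore be conditional on that rule. A proportional-odds model for each item does not need it.

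**Conclusion.** The point holds as a cheap improvement to one exploratory endpoint: the analysis stated in the protocol SAP and sSAP is weaker than the collected data allow. It does not affect the primary hypothesis or the interim decision.

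The power range is conditional. It assumes that the pain scale's 0.5 SD carries over to an EHP-5 total, that 70 per arm supply both forms, and the correlations shown. At 0.2 SD, power is only 25–31% on the change-score scaling, so the case rests on obtaining an estimate with an interval and not on promised significance.

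Three stronger readings are tempting and should not be drawn.

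- *Near-certain power of 97–100%.* This puts 0.5 SD on every item. With inter-item correlations of 0.4–0.6 the sum then has an effect of 0.5 × √(5/(1+4r)) = 0.61–0.69 SD, larger than the plan's pain effect.
- *A large power gain over reading one item as any improvement.* No document plans that reading or any test on EHP-5, so there is no planned baseline for a gain.
- *Hopelessly sparse tables.* A Visit 3 by Visit 6 layout split by arm would have 5 × 5 × 2 × 5 = 250 cells in all, or 140/50 = 2.8 women per cell for each item. That layout is inferred. A response-by-arm table at one visit would have 10 cells averaging 14 women.

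**What to change.** Amend sSAP Section 3.6.1 before unblinding.

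- For each item, fit a proportional-odds model of the Visit 6 category with Visit 3 category, stratum and treatment. Report the odds ratio and 95% CI.
- Code the items 0–4 and form the five-item score, subject to the instrument's scoring rule. Analyse the Visit 6 score by ANCOVA with Visit 3 score, stratum and treatment. Report the difference and 95% CI.
- State how Discontinuation-visit forms and missing Visit 6 forms are used.
- Note that the EHP-5 baseline is Visit 3 with a four-week recall. It therefore reflects the time before the placebo run-in, not the Baseline Cycle used for pain.
- Label these estimates exploratory and unadjusted for multiplicity.
- Keep the cross-tables as description, split by arm, and define their rows and columns.
- If the separate plan for participant-reported outcomes already contains such an analysis, cross-refer to it here instead.

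The cost is wording and a few lines of code, with no new data. The downside is a few more unadjusted exploratory estimates.

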
 • To evaluate the efficacy of MK-7264 as measured by the proportion of participants with at least 1-point reduction in average daily pelvic pain score (cyclic and non-cyclic, combined and separately) as compared to baseline during TRC2 and 
 • Irrespective of analgesic use • With no increase in average daily use of rescue medication by number of tablets • With no increase in average daily use of rescue medication and no use of concomitant pain medication • With no increase in average daily use of rescue medication and no use of concomitant pain medication for ERP 	
 • Daily pelvic pain score • Use of naproxen sodium rescue medication • Use of concomitant pain medication

Objectives	Endpoints

 To evaluate the efficacy of MK-7264 versus placebo in reducing average daily pelvic pain (cyclic and non-cyclic, combined and separately) during Treatment Cycle 1 (TRC1) as measured by an NRS in the daily eDiary 	
 Daily pelvic pain score

 To evaluate average daily pelvic pain (cyclic and non-cyclic, combined and separately) during the Post-treatment Cycle (PTC) after the completion of TRC2, compared to the Screening Cycle (SC) 	
 Daily pelvic pain scores

 To assess the PGIC rating, the impact scores of pelvic pain and Endometriosis Health Profile-5 (EHP-5) on health-related quality of life during TRC 2 	
 PGIC ratings Impact score of pelvic pain EHP-5

 To evaluate the exposure-response relationship for endometriosis-related pain and taste disturbance 	
 Plasma exposure of MK-7264 Daily pelvic pain scores (cyclic and non-cyclic, combined and separately) Taste-related AEs

 To explore the relationship between genetic variation and response to the treatment(s) administered, and mechanisms of disease. Variation across the human genome may be analyzed for association with clinical data collected in this study. 	
 Germline genetic variation

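### The sSAP analyses the exploratory seven-category PGIC only as improved versus not improved, so the order of the ratings goes unused; an ordinal comparison should be added

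*Combined protocol and SAP*

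**What the plan says.** Protocol Section 3 places the PGIC rating among the tertiary/exploratory objectives. Protocol 4.2.1.1 states: "The PGIC is an exploratory endpoint, to be assessed at the end of TRC2". It adds: "It is a 7-point scale in the eDiary to collect" the participant's rating of overall change.

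sSAP 3.6.1 lists the seven responses, from much better, through the same, to much worse. It then defines one analysis variable: "Proportion of subjects with improvements (either 'much better' or 'better' or 'a little better' on the PGIC scale"). That proportion "at TRC2 will be analyzed using the stratified Miettinen and Nurminen method (1985").

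Nothing else is specified there for the PGIC. The same section treats other graded outcomes more fully: each EHP-5 item is tabulated over all its response levels, and the pain-score responder endpoints are analysed at reductions of 1, 2 and 3 points.

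The only effect size and power in the documents concern the pelvic pain score. sSAP 3.9 says that "140 evaluable participants (70 participants in each group) will provide 84% power to detect a difference of 1 point between MK-7264 and placebo", with an SD of 2. Protocol Section 9 also announces a separate analysis plan for participant-reported outcomes, which is not among the documents.

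**The concern.** The endpoint is the rating, an ordered scale. Once the top three categories are pooled, a woman who is much better counts the same as one who is a little better, and a woman who is unchanged counts the same as one who is much worse. A treatment effect that moves women within the improved range, or within the not-improved range, adds nothing to the planned comparison.

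What is at stake is how well a supportive endpoint can show a difference. The protocol's Introduction cites PGIC improvements as supportive evidence from the osteoarthritis trial, whose primary objective was not met. Readers of this proof-of-concept trial may look to the PGIC in the same way.

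**Working it through.** **Inputs from sSAP 3.9 (pain score only).** 70 evaluable per arm, difference 1, SD 2, so a standardised effect of 1/2 = 0.5; two-sided 5%.

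**Inputs assumed, because the documents give none for the PGIC.** The ratings are cut from a latent normal variable. Treatment shifts it by 0.5 SD (carried over from the pain score), or by less. Between 30% and 70% of placebo women report improvement.

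**Step 1: reproduce the plan's figure.** Power = Φ(1/(2√(2/70)) − 1.96) = Φ(2.958 − 1.96) = 84.1%. The stated 84% is right for the pain score.

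**Step 2: power of the dichotomised comparison.** If a share p of placebo women improve, the active share is q = Φ(Φ⁻¹(p) + 0.5). With m = (p + q)/2,

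power ≈ Φ{[(q − p) − 1.96√(2m(1 − m)/70)] / √([p(1 − p) + q(1 − q)]/70)}.

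For p = 0.40: q = Φ(−0.253 + 0.5) = 0.597 and m = 0.4985. The two standard errors are 0.0845 and 0.0829. Power = Φ((0.197 − 0.1656)/0.0829) = Φ(0.38) = 65%.

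**Step 3: compare with an ordinal test.** 40,000 simulated trials per row. The ordinal test is the Wilcoxon with tie correction. The binary test is the unstratified Miettinen-Nurminen score test on the top three categories. Placebo distributions are spread over all seven categories; for example, at 40% improved, from worst to best: 3, 7, 12, 38, 22, 13 and 5%.

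| Placebo improved | Active improved | Ordinal power | Binary power | Gain (points) |
|---|---|---|---|---|
| 30% | 49% | 79% | 63% | 16 |
| 40% | 60% | 80% | 66% | 14 |
| 50% | 69% | 80% | 63% | 17 |
| 60% | 77% | 80% | 62% | 18 |
| 70% | 85% | 79% | 56% | 23 |

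**Step 4: vary the assumptions.**
- *Placebo shape at shift 0.5.* The improved share fixes only one of six cut-points. With placebo ratings concentrated in 'a little better' and 'the same', the gain is 9 to 12 points at 40% improved (binary 65%, ordinal 74% to 77%), 14 at 55% and 20 at 70%. Another pair of shapes gave 13 to 24. Overall: about 9 to 24.
- *Smaller shift.* At 0.35 the gain is 12 and 16 points (placebo 40% and 70%, spread distributions). At 0.25 it is 7 and 9 points with the spread distributions, 3 to 5 with the concentrated ones at 40%, and up to 10 elsewhere. Overall at 0.25: about 3 to 10.
- *Proportional odds instead of latent normal.* With log odds ratio 0.5π/√3 = 0.907, the gain is 10, 8, 12, 16 and 25 points at 30, 40, 50, 60 and 70%.
- *Stratification.* With 30% in the severe stratum and a 0.5 SD difference between strata (both assumed), the van Elteren test has 80, 80, 79 and 77% power at 30, 40, 55 and 70% improved. A stratified test of proportions has 63, 65, 61 and 55%. The gap stays at about 15 to 22 points.

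**Step 5: is the position of the cut to blame?** Counting only 'better' and 'much better' as improved, at shift 0.5 and under the latent-normal model of step 3, changes binary power as follows.

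| Placebo in top three categories | Planned cut | Stricter cut |
|---|---|---|
| 30% | 63% | 52% |
| 40% | 66% | 58% |
| 50% | 63% | 62% |
| 60% | 62% | 64% |
| 70% | 56% | 66% |

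The stricter cut does worse up to 50% and better only from about 60%. No row reaches the 79% to 80% of the ordinal test.

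**The case against.** The case for leaving the plan alone has real weight. The PGIC is exploratory, with no hypothesis, no power claim and no multiplicity role. A stratified difference in the proportion improved is valid and easy to read. The separate plan for participant-reported outcomes may already contain an ordinal analysis. All of that stands. It limits the consequence but does not supply a reason to leave the order of the ratings unused when the data are collected anyway. Protocol 9.6 assigns the methods for exploratory objectives to the supplemental SAP, so sSAP 3.6.1 is the text to amend or cross-reference.

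A reader might infer several stronger points that the documents do not support:
- *That power is lost at the trial's own assumed effect.* The 1 point and SD of 2 describe a cycle-averaged diary score. The trial assumes nothing about the PGIC, and carrying over 0.5 is an assumption of this check.
- *That counting 'a little better' as improved is the fault, because placebo response is highest there.* Step 5 shows the cut is not the cause. The documents give no placebo PGIC rate, and the run-in is meant to exclude women whose average pain falls below 5 on placebo.
- *That the PGIC is the main check on whether a pain change matters to the participant.* Protocol 4.2.1.1 groups it with the EHP-5 and the impact questions, and approaches clinical importance through the 1-, 2- and 3-point reductions.
- *That no other PGIC analysis is planned.* Only the sSAP can be checked.

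**Conclusion.** The concern holds as a worthwhile, low-cost improvement to an exploratory analysis. The sSAP reduces seven ordered categories to two, and the ordinal test was more powerful in every scenario tried.

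The size is conditional. With 70 per arm, two-sided 5% and a latent-normal shift, the gain is roughly 9 to 24 points if 0.5 SD carries over and 30% to 70% of placebo women report improvement, and about 3 to 10 points at 0.25 SD. The direction is firmer than the amount, which depends on an effect and a placebo distribution that the documents do not give. The planned comparison is not blind to an effect: at 0.5 SD it keeps 56% to 66% power across the rows of step 3. The 84% stated for the primary endpoint is correct and unaffected.

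**What to change.** In sSAP 3.6.1, under the PGIC:
- add an ordinal comparison of all seven categories, stratified by baseline pain stratum: a van Elteren test, or a proportional-odds model with treatment and stratum;
- report the number and percentage in each category by arm;
- keep the proportion with any improvement, with its Miettinen-Nurminen interval, as a supplementary display;
- if the separate participant-reported-outcomes plan already contains an ordinal analysis, cross-reference it instead.

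This costs a few sentences and one procedure call, and needs no new data. Protocol Section 9 allows exploratory analyses to be changed through the sSAP before unblinding and database lock. A rank measure or odds ratio is slightly harder to read than a risk difference, which is why the proportion should stay. The proportional-odds version also adds a model assumption that the van Elteren test avoids.
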